Appendix B: Schedule of Procedures

Table 13.	Schedule of Procedures: Parts A, A2, and B
Table 14.	Schedule of Procedures: Parts C1 and C2
Table 15.	Schedule of Procedures: Parts D1 and D2
Table 16.	Schedule of Procedures: Parts E1 and E2
Table 17.	Schedule of Vital Signs Measurements: All Parts
Table 18.	Schedule of PK and ADA Assessments: Parts A and A2
Table 19.	Schedule of PK and ADA Assessments: Part B
Table 20.	Schedule of PK and ADA Assessments: Part C1
Table 21.	Schedule of PK and ADA Assessments: Parts C2
Table 22.	Schedule of PK and ADA Assessments: Part D1
Table 23.	Schedule of PK and ADA Assessments: Part D2
Table 24.	Schedule of PK and ADA Assessments: Part E1
Table 25.	Schedule of PK and ADA Assessments: Part E2

Table 13. Schedule of Procedures: Parts A, A2, and B

Page 1 of 4

Period/ Procedure	Screening	Treatment Period											FU/EOS ²⁵
		Cycle 1 DLT Assessment Day 1 to Day 21			Cycle 2			Cycle 3 & On ²²			EOT ²⁴		
Study/Visit Day ¹	-30 to 0	1	4 ²³ (±1d)	8 (±2d)	15 (±2d)	1 (±2d)	8 (±2d)	15 (±2d)	1 (±2d)	8 (±2d)	15 (±2d)	(±7d)	Refer to Footnote
Informed consent	X												
Medical history ²	X												
Demographics	X												
AE assessment ³		X		X	X	X			X			X	
Concomitant medications ⁴	X	X		X	X	X			X			X	
HIV/CMV/ Hepatitis B, C	X												
CX-2009 administration ⁵		X				X			X				
CT/MRI (chest, abdomen, pelvis) ⁶	CT/MRI/Tumor assessment to be conducted every 8 (±1) weeks from the first dose of CX-2009 with assessment for response per RECIST Version 1.1												
Bone scan ⁷	As clinically indicated												
ECG ⁸	X	Day 1 of Cycles 1 and 3 and as clinically indicated for other visits										X	
Full physical examination ⁹	X											X	
Targeted physical examination ¹⁰		X		X	X	X			X				

Table 13. Schedule of Procedures: Parts A, A2, and B

Page 2 of 4

Period/ Procedure	Screening	Treatment Period											FU/EOS ²⁵
		Cycle 1 DLT Assessment Day 1 to Day 21			Cycle 2			Cycle 3 & On ²²			EOT ²⁴		
Study/Visit Day ¹	-30 to 0	1	4 ²³ (±1d)	8 (±2d)	15 (±2d)	1 (±2d)	8 (±2d)	15 (±2d)	1 (±2d)	8 (±2d)	15 (±2d)	(±7d)	Refer to footnote
Complete ophthalmology examination ¹¹	X	All subjects within 5 days prior to Cycle 1, Day 1; Cycle 2, Day 1; Cycle 3, Day 1; and at the EOT Visit. Subjects who report treatment-emergent changes in vision or other ocular symptoms will undergo repeat examinations prior to infusion every other cycle and as clinically indicated.											
Ocular symptom assessment ¹²	X	X				X			X			X	

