13.1.1 Primary Efficacy Endpoint

The ORR is the primary efficacy endpoint. For solid tumors, response evaluation will be based on the RECIST criteria (v1.1) and ORR is defined as the proportion of subjects with complete response (CR) or partial response (PR) on two consecutive tumor assessments with scan dates at least 4 weeks apart according to RECIST (RECIST v1.1).

The primary efficacy analysis will be based on the REP. Exact 2-sided 95% Cis (using the Clopper-Pearson method) will be calculated for all proportion estimates.

A listing of tumor data including total tumor burden, RECIST v1.1 response assessments (target lesion evaluation, non-target lesion evaluation, and overall subject response) will be provided.

Response Assessment and Best Overall Response – RECIST v1.1

Efficacy outcomes will be summarized by dose level and by cancer type using RECIST v1.1 among the REP. The overall number of subjects for each dose; and the number, proportion, and 95% exact 2-sided CI (using the Clopper-Pearson method) of confirmed CR and PR, unconfirmed CR and PR, SD, PD, not evaluable (NE), overall response (CR + PR), disease control (CR + PR + SD) will be calculated. A summary table of the above response assessments by part using RECIST v1.1 among the REP will be provided. A swim lane plot of response assessment status over time using RECIST v1.1 will be produced.

The best overall response is the best response recorded from the start of study treatment until the end of treatment taking into account any requirement for confirmation. If the best overall response is determined before the end of treatment (e.g., for an interim data cut), then it is the best response recorded from the start of study treatment until the date of the data cut.

When no imaging/measurement is done at all at a particular time point, the subject is not evaluable (NE) at that time point. If only a subset of lesion measurements are made at an assessment, usually the case is also considered NE at that time point, unless a convincing argument can be made that the contribution of the individual missing lesion(s) would not change the assigned time point response (as may happen in the case of an assessment of PD).

Complete or partial responses may be claimed only if the criteria for each are met at a subsequent time point as specified in the protocol (i.e., ~8 weeks later and no

earlier than 4 weeks later). In this circumstance, the best overall response can be interpreted as in Table 1.

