13.1.2 Secondary Efficacy Endpoints

Secondary efficacy endpoints are:

- DOR,
- TTR,
- PFS, and
- OS.

Time-to-Event Endpoints

DOR

DOR is defined as the time from the date of the first documentation of objective tumor response (i.e., ORR = CR or PR) that is subsequently confirmed to the date of the first documentation of objective disease progression or death due to any cause, whichever occurred first. DOR is only calculated for subjects in the REP who have a confirmed objective tumor response. Subjects who neither progress nor die will be censored on the date of their last tumor assessment.

Table 2 Date of Censoring – DOR

| Description of Situation | Date of Progression or Censoring | Outcome |
|---|---|----------------|
| No disease progression nor death on-study | Date of last tumor assessment | Censored |

TTR

TTR is defined as the time from the date of the first dose of study drug to first documentation of confirmed objective tumor response. TTR is only calculated for subjects in the REP.

PFS

PFS is defined as the time from the date of the first dose of study drug to the date of first documentation of objective tumor progression (i.e., PD) or death due to any cause, whichever occurs first. Subjects who die without a reported progression will be considered to have progressed on the date of their death. Subjects who did not progress or die will be censored on the date of their last tumor assessment. Subjects who did not have any on-study tumor assessments and did not die will be censored on their date of first dose of study treatment. Subjects who started anti-cancer therapy without a prior reported progression will be censored on the date of their last tumor assessment prior to the initiation of subsequent anti-cancer therapy. PFS is calculated for using the SP.

Table 3. Date of Progression or Censoring -- PFS

| Description of Situation | Date of Progression or Censoring | Outcome |
|---------------------------------|---|----------------|
| No baseline disease assessments | Date of first dose of study drug | Censored |

| | | |
|---|---|------------|
| Death before first disease assessment | Date of death | Progressed |
| No disease progression nor death on-study | Date of last tumor assessment with a response assessment other than not evaluable | Censored |
| Death without a reported progression | Date of death | Progressed |
| No on-study tumor assessments and did not die | Date of first dose of study drug | Censored |

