Estimates of time-to-event endpoints (DOR, TTR, PFS, and OS) will be obtained using the Kaplan-Meier method. Kaplan-Meier curves will be provided for these endpoints. A swim lane plot will be provided for DOR. DOR and TTR will also be summarized using descriptive statistics for confirmed objective responders.

The median, and 95% CIs around the DOR, TTR, PFS, and OS will also be calculated using the Kaplan-Meier method. The range of TTR, PFS and OS will be provided as well. Frequencies and percentages will be summarized for event rates and censored observations of the time-to-event endpoints. Six- and twelve-month and 2-year survival rates will be included as well. The number and percentage of disease progressions and deaths will be included (replacing the event rate) in the PFS summary.

CBR16 and CBR24

Breast cancer patients will also have CBR16 and CBR24 summarized by dose level and also by cancer subtype (TNBC, HR+/HER2-, HER2+). CBR16 is defined as the proportion of subjects with best overall response of CR or PR or with SD for at least 16 weeks. CBR24 is defined as the proportion of subjects with best overall response of CR or PR or with SD for at least 24 weeks. CBR16 and CBR24 will only be calculated for subjects in the REP.

SD Duration is defined as the time interval from the start of the treatment to the date of subsequent PD or on-treatment death. In the absence of PD or on-treatment death before the analysis cut-off date, it is the time from the start of treatment to the date of the last adequate tumor assessment before the cut-off date.

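### The DOR text and SAP Table 2 omit the exclusion of non-evaluable (NE) assessments that Table 3 applies to PFS, so a trailing NE assessment can lengthen a responder's censored DOR

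*SAP*

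**What the plan says.** All the rules are in SAP section 13.1.2.

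- **DOR paragraph:** "Subjects who neither progress nor die will be censored on the date of their last tumor assessment".
- **Table 2 (DOR), its only row:** "No disease progression nor death on-study | Date of last tumor assessment | Censored".
- **PFS paragraph:** "Subjects who did not progress or die will be censored on the date of their last tumor assessment". Its sentence on subjects who start another anti-cancer therapy also has no evaluability condition.
- **Table 3 (PFS), row for no progression and no death on study:** "Date of last tumor assessment with a response assessment other than not evaluable". The same condition appears in two further rows, for new anti-cancer therapy and for death or progression in follow-up.
- **Duration of stable disease**, same section, uses a third wording when there is no event: "it is the time from the start of treatment to the date of the last adequate tumor assessment before the cut-off date".

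SAP section 13.1.1 explains how an assessment becomes NE. One route is that nothing was imaged or measured. The other is partial measurement: "If only a subset of lesion measurements are made at an assessment, usually the case is also considered NE at that time point".

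The scan schedule in Protocol Appendix B reads "CT/MRI/Tumor assessment to be conducted every 8 (±1) weeks from the first dose of CX-2009". It moves to every 12 weeks for subjects on study drug for more than 12 months, with a further scan at the end-of-treatment visit if the subject has not progressed.

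DOR is estimated by Kaplan-Meier and shown in a swim lane plot. In addition, "DOR and TTR will also be summarized using descriptive statistics for confirmed objective responders".

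**The concern.** An NE assessment gives no evidence that a response was still present. If DOR is censored there, the subject counts as event-free in response over an interval when response was not observed. Table 3 avoids this for PFS, and the stable-disease rule avoids it by asking for an adequate assessment. DOR has no such safeguard in either its paragraph or its table.

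Two things are at stake. Response time may be credited that nobody observed. And one responder may appear in the same report with two different last progression-free dates, one for PFS and a later one for DOR. Separately, the PFS paragraph and Table 3 give a programmer two different instructions for PFS.

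**Working it through.** The plan gives no figure that depends on this rule, so there is none to reproduce. The check compares the rules and then applies them to assumed cases.

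**1. The rules side by side** (responder with no progression, no death and no new therapy)

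| Place in SAP 13.1.2 | Censoring date | NE excluded? |
|---|---|---|
| DOR paragraph | latest assessment | no |
| Table 2 (DOR) | latest assessment | no |
| PFS paragraph | latest assessment | no |
| Table 3 (PFS) | latest assessment not graded NE | yes |

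**2. Does another passage supply the condition for DOR?** No. Section 11.3 of the Core has the same unqualified DOR wording, and Protocol section 9.2 lets the SAP override the Core in any case. The SAP's note on scan dates, after Table 4, fixes the dates of response and progression, not of censoring.

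**3. Can the case arise?** Yes, by the partial-measurement route, where a dated assessment exists but is graded NE. Where nothing was imaged, there is no scan date to extend to.

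**4. One responder (assumed).** Scans every 8 weeks, partial response at week 8, confirmed at week 16, then k NE assessments and no event.

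- PFS under Table 3 is censored at week 16.
- DOR under Table 2 ends at week 16 + 8k, so DOR = (16 + 8k) − 8 = 8 + 8k weeks.
- DOR under Table 3's condition = 16 − 8 = 8 weeks for any k.
- Excess = 8k weeks.

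| k | DOR ends, Table 2 (week) | DOR, Table 2 (weeks) | DOR with NE excluded (weeks) | Excess (weeks) |
|---|---|---|---|---|
| 0 | 16 | 8 | 8 | 0 |
| 1 | 24 | 16 | 8 | 8 |
| 2 | 32 | 24 | 8 | 16 |
| 3 | 40 | 32 | 8 | 24 |

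After month 12 the step is 12 weeks. An end-of-treatment scan falls off this grid and may add less.

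**5. Two responders.** Protocol section 1.3.4.2 reports 2 confirmed partial responses among 92 response-evaluable subjects at 30 November 2019.

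- Both have events: the rule changes nothing.
- Both are censored: the Kaplan-Meier median is not reached under either rule.
- One event, one censored: the curve changes only if the added time carries the censored subject past the event time. The drop at the event is then to 1 − 1/2 = 0.5 instead of 1 − 1/1 = 0.

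The descriptive summary of durations takes in the added time directly whenever a censored responder has a trailing NE assessment.

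**6. Direction of effect (assumed set of eight responders).** Events at 8, 16, 24, 32 and 40 weeks; three censored, each with one trailing NE assessment. Censored times are 8, 16, 16 with NE excluded, and 16, 24, 24 under Table 2.

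- NE excluded: S(8) = 7/8 = 0.875; S(16) = 0.875 × 5/6 = 0.729; S(24) = 0.729 × 2/3 = 0.486. Median 24 weeks. Mean = (120 + 40)/8 = 20 weeks.
- Table 2: S(8) = 0.875; S(16) = 0.875 × 6/7 = 0.75; S(24) = 0.75 × 4/5 = 0.6; S(32) = 0.6 × 1/2 = 0.3. Median 32 weeks. Mean = (120 + 64)/8 = 23 weeks.

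This set was chosen to show direction. It does not estimate the effect in this trial.

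**The case against.** The SAP nowhere says that an NE assessment counts towards DOR. The PFS paragraph uses nearly the same unqualified sentence as the DOR paragraph, and Table 3 then refines it, so the phrase may be shorthand in both places. This stands as a caution: the contrast between DOR and PFS rests on Table 3 alone, and the effect follows from an omitted condition. It does not dispose of the point, because Table 2 is the DOR counterpart of Table 3 and does not refine the phrase.

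A reader might also infer that DOR and PFS share one progression event, so that a common censoring phrase would make them end on the same date. The documents do not support that. Table 3 censors PFS at new anti-cancer therapy and for death or progression in follow-up. Table 2 has no such rows, and the DOR definition counts progression or death from any cause. DOR can therefore outlast PFS for reasons unrelated to NE assessments.

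The objection on size also stands. The effect needs a responder without an event whose last assessment was performed but graded NE, and no document says how often that occurs. DOR is secondary and carries no hypothesis test. Only 3 of the 99 treated subjects were in Part B (SAP section 4.2), the one enrolled part with a primary efficacy objective.

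**Conclusion.** The point holds as a minor defect of wording with a possible effect on results. Followed literally, Table 2 and the DOR paragraph allow censored DOR to run beyond the last date on which response was observed. The excess is up to about one scan interval (8 weeks, or 12 weeks after month 12) for each trailing NE assessment, assuming scans are on schedule. No event date moves. The PFS paragraph also conflicts with Table 3.

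A reader might conclude from the small number of responders that a single such case must shift the DOR estimate. That goes too far. With two responders the Kaplan-Meier curve changes only in the one configuration shown above, though the descriptive summary is more exposed. The count of 2 comes from a November 2019 cut, and the final number of confirmed responders is not in the documents. The size of the effect in this trial therefore cannot be stated.

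**What to change.** In Table 2, in the DOR paragraph and in the PFS paragraph (including its sentence on subsequent anti-cancer therapy), define the censoring date with Table 3's phrase, "Date of last tumor assessment with a response assessment other than not evaluable". For subsequent therapy, keep the existing restriction to assessments made before that therapy began. The cost is a few words in the SAP, with no new data; it is best done before database lock.

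This closes the NE discrepancy only. The SAP should also say whether it is intended that DOR, unlike PFS, is not censored at new anti-cancer therapy or for death or progression in follow-up, so that readers do not expect the two endpoints to end on the same date.

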4.3 Study Periods and Follow-Up

The study is divided into periods with associated evaluations and procedures that must be performed at specific time points. The schedule of procedures in Appendix B of the CTMX-M-2009-001 Protocol Module summarizes the frequency and timing of efficacy, safety, and other study measurements. Refer to the Common Core Document for a description of each procedure.

As with any Phase 1 study, an individual subject's participation in the study is difficult to predict. It is estimated that average treatment will last approximately 6 months, followed by Follow-Up contact every 3 to 6 months for another 1 to 2 years, or as long as the subject remains alive (Figure 3).

Figure 3: Study Periods

Notes: An EOT Visit will be conducted 30 days (± 7 days) after the last infusion of study treatment. Follow-Up: If subject has not had progression, imaging assessments will continue until progression is documented. If subject had documented progression, the subject will continue in survival Follow-Up Visits every 3 months (± 14 days) after the EOT Visit for 1 year and then every 6 months (± 14 days) (this may be by telephone), or until death. Subsequent cancer treatment will be collected. Survival Follow-Up will be done every 3 months (± 14 days) as described above.

DLT = dose-limiting toxicity; EOT = end of treatment; IV = intravenous; q14 = every 14; q21 = every 21.

Following the completion of study treatment, subjects with progressive disease per RECIST v1.1 as measured by investigator assessment, will return for an end of treatment (EOT) Visit and then enter the Follow-Up Period for monitoring of survival. Subjects who for other reasons stop study drug treatment and subjects with stable disease, confirmed partial response, or confirmed complete response will enter the Follow-Up Period for monitoring of DOR and PFS.

The study will be completed approximately 2 years from the date the last subject is enrolled or when the last subject has completed treatment and the last Follow-Up Visit.

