| Subjects who started anti-cancer therapy without a prior reported progression | Date of their last tumor assessment with a response assessment other than not evaluable prior to the initiation of subsequent anti-cancer therapy | Censored |
| Died or progressed (on treatment*) after a missed assessment | Date of death or disease progression | Progressed |
| Died or progressed in follow-up | Date of last tumor assessment with a response assessment other than not evaluable | Censored |

* Subjects who discontinued the study 30 or fewer days from the last dose of study drug are considered to have discontinued the study during the treatment period. Subjects who discontinue the study more than 30 days after the last dose of study drug are considered to have discontinued the study while in follow-up.

OS

OS is defined as the time from the date of the first dose of study drug to the date of death due to any cause (as captured on the Study Discontinuation, Treatment Termination, Substudy Discontinuation, Survival Status and/or AE CRF pages). Two analyses of OS will be conducted. The first will analyze all on-treatment deaths (deaths occurring within 30 days of last dose of study drug) while the second will analyze all on-study deaths (deaths occurring after first dose of study drug while on study). Subjects who are last known to be alive and/or lost to follow-up are censored at the date of last contact (as captured on the Discontinuation Call, Study Discontinuation, Treatment Termination, Survival Status, and/or Substudy Discontinuation CRF pages). Interim analyses of OS would use the data cut date as the censoring date of last contact if the subject is last known to be alive and/or lost to follow-up. OS is calculated for using the SP.

Table 4. Date of Censoring

| Description of Situation | Date of Progression or Censoring | Outcome |
|---|----------------------------------|----------|
| Last known to be alive and/or lost to follow-up | Date of last contact | Censored |

Please note that the scan date of the tumor assessment associated with the reported response assessment will be used as the tumor response date referenced above (i.e., first documentation of objective tumor response, first documentation of objective disease progression, and first documentation of objective tumor progression).

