13.1.3 Efficacy Measures during Follow-up

Following the completion of study treatment, subjects with progressive disease will enter the follow-up period for monitoring of survival; subjects with SD, PR, or CR will enter the follow-up period for monitoring of DOR and PFS. Once a subject experiences progressive disease, they will continue to be monitored for survival.

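### SAP Table 3 censors first progression or death in follow-up, against the SAP's own PFS definition, another row of the same table and the stated purpose of follow-up

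*SAP*

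**What the plan says.** In SAP 13.1.2, PFS runs from first dose to first documented progression or death from any cause, whichever is earlier. The narrative adds: "Subjects who die without a reported progression will be considered to have progressed on the date of their death". It lists three reasons for censoring: no event, no on-study tumor assessment, and new anti-cancer therapy before progression. Follow-up is not among them.

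Table 3 carries this over in the row "Death without a reported progression | Date of death | Progressed". Its last row then reads "Died or progressed in follow-up | Date of last tumor assessment with a response assessment other than not evaluable | Censored".

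Table 2, for DOR, has a single censoring row: "No disease progression nor death on-study | Date of last tumor assessment | Censored". It has no counterpart to the last row of Table 3.

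On follow-up itself, SAP 4.3 says that subjects who stop drug for reasons other than progression "will enter the Follow-Up Period for monitoring of DOR and PFS", and that imaging continues until progression is documented. SAP 13.1.3 repeats that "subjects with SD, PR, or CR will enter the follow-up period for monitoring of DOR and PFS". Core 9.9.2 likewise asks that progression be documented, where possible, after drug is stopped.

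**The concern.** The definition and the table cannot both be programmed. For a subject who stops drug without progression, a later first progression or death is an event by the definition and a censored observation by the last row. For deaths, two rows of the same table disagree. The rule in Protocol 9.2 ranks the SAP above the Core; it does not rank one part of the SAP above another.

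The term that triggers the row is also not tied to the event date. The Table 3 footnote sets a 30-day boundary, but for leaving the study: subjects who leave later are "considered to have discontinued the study while in follow-up". SAP 4.3 instead places follow-up after the end-of-treatment (EOT) visit: subjects with progression "will return for an end of treatment (EOT) Visit and then enter the Follow-Up Period".

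At stake are the Kaplan-Meier PFS estimates and the counts of progressions and deaths planned for the PFS summary. The SAP's purpose section says its analyses may support publications and FDA submissions. Subjects who stop for toxicity or clinical decline may differ in prognosis, so the censoring may be informative.

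**Working it through.** The documents give no PFS median, event count or power, so there is no figure to reproduce. The check has two parts.

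**1. Test cases against the text**

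- *Death without progression, after the EOT visit and more than 30 days after last dose.* Definition: event at death. Row on death without reported progression: event at death. Last row: censored at the last evaluable scan. If there was no on-study scan, the row for death before the first disease assessment also makes it an event, and the last row has no post-baseline scan to censor at.
- *Stable disease at week 8, drug stopped for toxicity, first progression at week 16 in follow-up.* Definition: event at week 16. Last row: censored. The date is unclear, because the week-16 scan is itself an evaluable assessment; it could be that scan or the one before. In a confirmed responder, the same kind of follow-up progression is an event for DOR.
- *Progression on an EOT scan at days 31 to 37 after last dose* (the visit is at 30 ± 7 days). This is past a 30-day cut but not yet in follow-up under SAP 4.3.
- *Progression documented on treatment.* Already counted, so unaffected.

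**2. Direction and size**

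Suppose n subjects are at risk at an event time, with d events, f of them in follow-up. The Kaplan-Meier factor is 1 − d/n by the definition. If the f subjects were censored at an earlier scan, it becomes 1 − (d − f)/(n − f), which is larger whenever n > d. Between that earlier scan and the event, the smaller risk set pulls the curve down slightly. The net effect is generally upward, but this is not guaranteed in a small group.

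*Simulation A* (8,000 subjects per scenario, 80 scenarios, all inputs assumed):

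- first event exponential with median 1.5, 2, 3, 4 or 6 months; 15% or 30% of first events are deaths without progression;
- 10%, 20%, 30% or 40% stop drug at a random time before the event; 0 or 50% of these start new therapy, censored identically under both rules;
- scans every 8 weeks ± 7 days (12-weekly after about 12 months) plus an EOT scan; follow-up begins after the EOT visit;
- each scenario is run with censoring at the prior scan and at the progression scan, giving 160 estimates.

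| Stop drug before progression | 6-month PFS overstated (points) | PFS events censored |
|---|---|---|
| 10% | 0.4–2.5 | 3–8% |
| 20% | 1.1–4.6 | 7–15% |
| 30% | 1.5–7.6 | 11–23% |
| 40% | 2.6–10.9 | 15–32% |

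None of the 160 differences at 6 months was negative. At 12 months they ran from +0.1 to +13.9 points. Median PFS moved by 0 to 2.3 months, typically 0.1 to 0.4.

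Example: median 3 months, 20% stopping, 15% deaths, 50% new therapy. Six-month PFS is 0.276 by the definition and 0.301 to 0.310 under the row: 0.301 − 0.276 = 0.025 and 0.310 − 0.276 = 0.034. In this example 8.7% of events are censored.

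*Simulation B* (20,000 subjects per scenario, different assumptions): median 12 weeks to progression and 40 weeks to death, 8-weekly scans, 104-week cutoff, no new therapy, follow-up taken as more than 30 days after last dose, censoring at the prior scan.

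| Median time to stopping drug (weeks) | Subjects with event: definition / row | Median PFS (weeks): definition / row |
|---|---|---|
| 13 | 100% / 60% | 13.5 / 16.0 |
| 26 | 100% / 75% | 13.3 / 15.6 |
| 52 | 100% / 86% | 12.5 / 13.6 |
| 104 | 100% / 92% | 12.6 / 13.2 |

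The row removes about 8% to 40% of events and lengthens the median by about 0.6 to 2.5 weeks.

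*Narrower reading*, with the row applied only after a missed follow-up scan, on the scenarios of Simulation A: −0.2 to +1.1 points with 10% of follow-up scans missed (0.3–5% of events censored), and −1.1 to +2.6 points with 30% missed (1–13%).

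**The case against.** The strongest counter-argument is that the last row belongs with the row above it, which deals with an on-treatment event after a missed assessment and whose asterisk leads to the footnote separating treatment from follow-up. Read as a pair, the last row would cover only follow-up events after a missed assessment, and the effect would be small. That may have been the intent, but the condition is written only in the row above.

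A second argument is that an on-treatment PFS was chosen deliberately, since table rows may override a general definition, as the new-therapy row does. But the new-therapy rule is also in the narrative, and this one is not. Where the SAP wants an on-treatment limit it says so: OS has separate on-treatment and on-study analyses, and stable-disease duration refers to on-treatment death.

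Three points stand:

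- Every simulated size rests on assumed inputs, and the largest median shifts come from the extreme case of long PFS with 40% stopping.
- The effect is modest beside sampling error. At a 6-month PFS of 0.276, an approximate uncensored 95% half-width, 1.96 × √(0.276 × 0.724/n), is 9 points for all 99 treated subjects, 19 for n = 22 (the 8 mg/kg group in Protocol 1.3.4.1) and 29 for n = 9 (7 mg/kg, same section).
- The Core's PFS text matches the SAP narrative on death without progression. This is evidence of intent, though not a rule that resolves the table.

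**Conclusion.** The concern holds. The contradiction is in the SAP's own text and needs no assumption. As written, the last row lowers the PFS event count and, in every scenario simulated for that reading, raised 6-month PFS. The overstatement is 0.4 to 10.9 points if 10% to 40% of subjects stop drug before progression, a share the documents do not give. If the row applies only after a missed scan, the change is between −1.1 and +2.6 points with up to 30% of follow-up scans missed. PFS is a secondary, descriptive endpoint with no test or threshold attached, so this should be fixed but does not threaten the primary ORR or the safety conclusions.

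**What to change.** Delete the last row of Table 3 from the main PFS analysis, so that first progression or death counts whenever it occurs. Keep the existing censoring at the last evaluable scan before new anti-cancer therapy.

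If an on-treatment or missed-assessment PFS is wanted, for instance because late deaths are learned of by telephone, keep it as a labelled sensitivity analysis. There, define follow-up by event date. After the EOT visit would agree with SAP 4.3; the 30-day cut used elsewhere in the SAP would also serve, provided one is stated. State any missed-assessment condition, and say whether a progression scan can itself be the censoring date. DOR needs no change.

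The cost is one table row and minor reprogramming. Follow-up imaging and survival contacts are already in the protocol, so no new data are needed. Reported PFS will be less favourable than under the row, and deaths long after the last scan will count at the date of death, as the definition already requires.
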